Participants randomized to Rehab+WL will complete the exercise-based cardiac rehabilitation program described above, as well as a behavioral weight loss intervention that incorporates evidence-based dietary practices for achieving weight loss.¹⁵ Specifically, the weight loss intervention will consist of 6 months of a high-intensity, on-site comprehensive lifestyle intervention which includes prescription of a moderately reduced-calorie diet and the use of behavioral strategies to facilitate adherence to diet and physical activity recommendations.¹⁵ Individual calorie goals will be adjusted to achieve a weight loss of at least 5-10% within the 6-month intervention timeframe. This level of weight loss, which is considered “successful weight reduction that leads to decreased risk for development of or amelioration of obesity-related medical conditions and cardiovascular risk factors,¹⁵” will be achieved through a combination of meal replacements, approved meal plans, and individual nutrition and behavioral counseling with the study registered dietitian (RD) who has experience working with middle-aged and older adults on diet behavior modification. This approach will help to maximize weight loss, as obesity treatment guidelines note that the use of meal replacements is associated with increased weight loss at up to 6 months, in comparison with a balanced deficit diet using only conventional food.¹⁵

Calorie-Restricted Diet: Diet plans will provide a caloric deficit of 500 kcals per day. Energy needs will be calculated based on formulas established by the Institute of Medicine. The lowest calorie level permitted will be 1,100 kcals for women and 1,200 kcals for men. The calorie distribution goal will be 25-35% from protein, <30% from fat, and 45-50% from carbohydrates, consistent with the Dietary Reference Intakes for Energy and Macronutrients.³⁹ Participants will be asked to consume 2 meal replacements per day (Premier Protein shakes and bars); provided by the study), along with one meal composed of traditional foods (low in fat, high in vegetables), and 1-3 snacks as needed (e.g., cereal bar, fruit, or vegetable). For the meal, patients will follow a weekly menu plan and recipes provided by the study. The food plan will be tailored to individual preferences and energy needs. Participants will be guided by the RD on their food purchasing and preparation of the meals and will be encouraged to consume only what is approved from the menu.

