Cardiovascular events and rehospitalizations will be assessed by staff masked to group assignment. Pertinent medical records will be obtained to confirm all events and procedures. Hospitalizations will be categorized using the Clinical Classifications Software system from the Agency for Healthcare Research and Quality (<https://www.hcup-us.ahrq.gov/toolssoftware/ccs10/ccs10.jsp>). The study physician (masked to group assignment) will adjudicate each outcome using standardized criteria.

Analytical Plan

Sample Size

Assuming that at least 50% of eligible patients will be interested in participating in the study and meet the full inclusion/exclusion criteria, we anticipate enrolling 1-2 participants per week. Based on a conservative dropout rate of 20%, we expect a final sample size of 16 per group. While this pilot study is not designed to provide sufficient statistical power to detect differences in the measured outcomes, we will obtain estimates of treatment efficacy and estimate the variability of outcome measures in this population to use in the design of a larger, more definitive trial.

Data Cleaning

We will examine the distributions of the outcome variables and the need for any transformations to approximate conditional normality for further analysis. Summary statistics will be calculated, including means, standard deviations, quartiles, and ranges for continuous variables, and counts and percentages for categorical variables. Range and validation checks will be performed on all variables in collaboration with study personnel. We will examine the distributions of all the variables, identify the potential outliers and influential points, and clean any unreasonable data.

Statistical Analyses

All randomized participants will be included in their original intervention group regardless of compliance with the study protocol (i.e., an “intent to treat” analysis). Chi-square tests will be used to assess group differences in retention and compliance rates. Longitudinal data for the outcome variables will initially be presented graphically (e.g., spaghetti plot) with individual trajectories over time. The graphical displays will help to highlight aggregate patterns of potential scientific interest and identify unusual values. The mixed-model repeated measures ANCOVA model will be used to determine whether Rehab+WL leads to greater improvements in CHD and neurovascular outcomes than Rehab alone. A

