- 8) Weight Loss: The risks of caloric restriction are small and include excessive weight loss. These risks will be minimized by the direct involvement of a registered dietitian and medical oversight by the study physician. To ensure safety of study participants, food plans will be tailored to individual preferences, the lowest calorie level permitted will be 1,100 kcals for women and 1,200 kcals for men, and calorie goals will be closely monitored to minimize rapid or excessive weight loss. Weight loss interventions also have the potential to increase risk of hypoglycemia and hypotension. To minimize these risks, study staff will contact the primary care provider of any participant treated with glucose- or blood pressure-lowering medications who develops symptomatic hypoglycemia or hypotension to discuss adjustment or discontinuation of these medications. If a primary care provider cannot be contacted in a timely manner, the study physician may elect to adjust these medications and the personal care provider will be notified by phone and in writing. We have previously completed 8 weight loss trials in a variety of populations with no reports of significant adverse effects.
- 9) Neurovascular Testing: Risks and side effects related to TCD monitoring include reaction from the gel and risk of skin irritation from the TCD headband. However, these are very rare occurrences and no adverse events associated with TCD usage have been reported in the literature. The ECG electrodes may also cause some skin irritation or a mild rash; however, this usually goes away without treatment once the electrodes are removed. Some people may experience discomfort from the finger cuff squeezing their fingers. If this occurs another finger can be used for the assessment. Some fatigue during the sit-stand tests is normal and some people may feel claustrophobic when the non-rebreathing mask is placed over their nose and mouth; if this discomfort persists or if the participant experiences pain, dizziness, or other medical problem, the test will be terminated. Study staff will assess for any signs of pain or intolerance throughout the testing procedure.

Medical Clearance

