The study physician and/or PI will personally review the relevant medical records to ensure inclusion/exclusion criteria are met and that it is safe for the participant to participate. Study results related to blood pressure, hemoglobin A1c, glucose, lipid, and other relevant lab values that are obtained during scheduled study visits will be provided to each participant's primary care provider in a form that clearly indicates abnormal values and ranges. When a cardiovascular event is discovered during the trial, the study physician will decide whether it is permissible for the participant to continue the intervention. If the intervention is discontinued for safety reasons, it may be resumed after consultation with the participant's primary care provider.

Medical Costs

This study will involve a partnership with the Cardiac Rehabilitation Program at WFBH. Costs to attend cardiac rehabilitation for 6 months will be provided for all study participants.

Study Incentives

Participants will be provided with \$50 for each study visit completed (\$150 total for completing all study visits). This incentive is designed to help offset the cost of traveling to/from the medical center for study-related visits and purchasing food or prepared meals in accordance with the individualized meal plans.

Confidentiality and Privacy

Confidentiality will be protected by collecting only information needed to assess study outcomes, minimizing to the fullest extent possible the collection of any information that could directly identify participants, and maintaining all study information in a secure manner. To help ensure participant privacy and confidentiality, only a unique study identifier will appear on data collection forms. Any collected patient identifying information corresponding to the unique study identifier will be maintained on a linkage file, store separately from the data. The linkage file will be kept secure, with access limited to designated study personnel. Following data collection subject identifying information will be destroyed at least six years after the study ends consistent with data validation and study design, producing an anonymous analytical data set. Data access will be limited to study staff. Data and records will be kept locked and secured, with any computer data password protected. No reference to any individual participant will appear in reports, presentations, or publications that may arise from the study.

Data and Safety Monitoring

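### The masking claimed for the event adjudicator is not supported by the duties the protocol gives the study physician

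*Combined protocol and SAP*

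**What the plan says.** Recurrent Events makes two masking statements. The first concerns staff: "Cardiovascular events and rehospitalizations will be assessed by staff masked to group assignment". The second concerns the adjudicator: "The study physician (masked to group assignment) will adjudicate each outcome using standardized criteria". Records are obtained to confirm events, and hospitalizations are coded with a named classification system.

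Three other duties are given to the study physician:

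- **Diet risks** (Potential Risks, item 8, Weight Loss). On the risks of caloric restriction: "These risks will be minimized by the direct involvement of a registered dietitian and medical oversight by the study physician".
- **Medication changes** (same item). For symptomatic hypoglycemia or hypotension: "If a primary care provider cannot be contacted in a timely manner, the study physician may elect to adjust these medications".
- **Continuation** (Medical Clearance). Once a cardiovascular event is discovered, "the study physician will decide whether it is permissible for the participant to continue the intervention".

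The diet belongs to one arm only (Behavioral Weight Loss Intervention): "Participants randomized to Rehab+WL will complete the exercise-based cardiac rehabilitation program described above, as well as a behavioral weight loss intervention".

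Subject Recruitment Methods refers to a single study physician, who is a co-investigator. Randomization lets study staff look up individual assignments in the study database and states no exception for the adjudicator.

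**The concern.** A physician responsible for the medical safety of a diet given in one arm would ordinarily learn who is on it. If that person also classifies events, masking depends on a separation that the protocol does not describe.

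Two things are at stake. The first is the accuracy of a stated design property, which would carry over into the trial report and into the larger trial that this pilot is meant to inform. The second is the credibility of the comparison of events between arms. The Background gives as part of the rationale that calorie restriction in the subacute period after a coronary event has not been studied enough for safety. Adjudicated events bear on that question, and knowledge of the arm could influence a borderline classification.

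**Working it through.** The point concerns roles, so the check sets the sections side by side. One short calculation gives the scale.

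**1. Does each duty reveal the arm?**

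| Duty of the study physician | Section | Who it can concern | Bearing on masking |
|---|---|---|---|
| Medical oversight of caloric-restriction risks | Potential Risks, item 8 | Rehab+WL only | Direct: oversight of individual participants would identify the arm |
| Adjusting glucose- or blood pressure-lowering drugs | Potential Risks, item 8 | Any participant on such drugs, when the primary care provider cannot be reached | Context only: possible in either arm, though listed as a safeguard for the weight loss intervention |
| Deciding on continuation after a cardiovascular event | Medical Clearance | Either arm, since all participants receive rehabilitation | Context only, but triggered by the same kind of event that is adjudicated |

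The conflict therefore rests on the first row.

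**2. Is it the same person?** The text says 'the study physician' throughout, and Subject Recruitment Methods identifies one. No second physician or events committee is named. That one person fills every role is a fair inference, but it is not stated outright.

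**3. Is the adjudicator protected in some other way?**

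- Randomization opens assignments to study staff without excluding the adjudicator.
- Recurrent Events describes no redaction of the records obtained.
- Organization of Study Visits does describe protection for visit assessors: participants are asked not to reveal their group. Nothing comparable is described for the adjudicator.

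**4. Scale.** Inputs: 40 randomized (Objectives); 20% dropout and 16 per group (Sample Size). Equal arms are an assumption.

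- The plan's own figure: 40 × (1 − 0.20) / 2 = 16 per group. It reproduces and agrees with equal arms.
- Randomized per arm: 40 / 2 = 20.
- Effect of one event classified differently: 1 / 20 = 5 percentage points of that arm's proportion.

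No sample size, power or error rate changes.

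**The case against.** The strongest reply has four parts.

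- **Only one duty is specific to an arm.** A reader might infer that all three duties require knowing the allocation. The documents do not support that. Medication changes can be made from symptoms and a drug list, and a decision on continuation can arise in either arm. This part stands.
- **Oversight may be remote.** The dietitian sets the plans, counsels, reviews the food logs and adjusts intake. The text does not say that the physician reviews individual diet participants. A reader might infer that the adjudicator is certain to be unmasked, or that the masking statement is proven false. That goes beyond the text. What remains is that the protocol claims masking, gives the same role a duty specific to one arm, and describes nothing that keeps the two apart.
- **Events are not the only safety data.** A reader might infer that adjudicated events are the trial's sole structured safety information. They are not. The protocol also schedules laboratory panels and cardiac biomarkers, repeats the PHQ-9 at follow-up, weighs diet-arm participants weekly, reports adverse events to the IRB and uses a safety board that meets twice a year. This part stands.
- **The consequence is small.** The primary aim is feasibility. Recurrent events are not among the listed primary, secondary, tertiary or exploratory outcomes, and no analysis of events by arm is specified. Masked staff, medical records, a coding system and standardized criteria all limit discretion. This lowers the stakes, but it does not supply the missing separation of roles.

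**Conclusion.** The point holds in limited form: the masking claimed for the adjudicator is not supported by the roles as written. It rests on the oversight of diet risks in one arm, on the inference that one study physician fills all the roles, and on the absence of any described safeguard. The medication and continuation duties are supporting context.

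The 5-point figure is a scale for one event, assuming 20 per arm. It does not show that any event would be misclassified. The documents give no event rate, so nothing can be said about how many events to expect. The feasibility outcomes and the listed efficacy outcomes are unaffected. The correction is still worth making, because the protocol states masking as a property of the design and the correction costs almost nothing.

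**What to change.** Reconcile Recurrent Events with Potential Risks (item 8) and Medical Clearance in one of two ways.

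1. **Separate the roles.** If an existing co-investigator without these duties is qualified, name that role as adjudicator. Supply event records stripped of arm, diet and counseling information, and block that person's access to assignments in the study database.
2. **Withdraw the claim.** Otherwise, delete the masking statement for the adjudicator in Recurrent Events and report events as adjudicated unmasked under standardized criteria.

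The protocol lists several co-investigators but does not say whether another of them is a suitable physician. Only the second option is therefore certain to need no new staff.

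The first option costs a wording change, a database permission and redaction of the event records. The second costs a wording change. Neither adds patients, visits or procedures, and the clinical oversight duties stay as they are.

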Patients who meet all inclusion/exclusion criteria and provide informed consent to participate will be randomized to Rehab only or Rehab+WL using a randomization scheme with blocking stratified by sex and obesity severity (BMI<30 vs. BMI≥30 kg/m²). Block size and the randomization sequences will be unknown to all other study personnel. Study staff will be able to access individual treatment assignments through the study database which will be managed in the secure, web-based application REDCap (Research Electronic Data Capture).³³

Study Interventions

Cardiac Rehabilitation

All participants will undergo standard exercise-based cardiac rehabilitation at a WFBH site which consists of three exercise sessions and one group health/nutrition education class per week for 12 weeks.³⁴ Participants also have one meeting with a dietitian, usually within the first 2 weeks of the program, to discuss dietary concerns and address issues noted in the dietary assessment. In order to provide sufficient time for adequate weight loss and ensure the necessary behavioral adaptations for long-term maintenance of lifestyle changes, all participants will undergo an additional 12 weeks of supervised cardiac rehabilitation for a total period of 6 months. Cardiac rehabilitation will be conducted by program staff (including exercise physiologists, nurses, and dietitians) with many years of experience in risk factor management and exercise prescription.

Exercise: Each exercise session lasts for 60 to 90 minutes and consists of 5-10 minutes of warm-up and cool-down activity; up to 30 minutes of aerobic exercise using a variety of modalities (e.g., walking laps on a track, cycle ergometry, treadmills, stair climbers); and 15-20 minutes of upper and lower body resistance exercises using Thera-Bands. An exercise physiologist creates an individualized plan based on

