Feasibility will be assessed in terms of the ability to 1) recruit study participants (i.e., total number randomized divided by total number eligible); 2) retain participants in the study for the full 6 months (i.e., the proportion of randomized participants who return for follow-up testing); and 3) obtain adequate compliance to the prescribed intervention (i.e., total number of exercise/counseling sessions attended divided by total number of sessions prescribed). We anticipate that at least half of the eligible participants will agree to participate and of those who do, <20% will drop out prior to the study end. We also expect to achieve a compliance rate of $\geq 80\%$.

Secondary Outcomes

Body weight will be measured using a digital scale. Additional measures of body size/habitus will also be obtained, including height (using a standard wall-mounted stadiometer).

The ***6MW test*** is a valid and reproducible measure of submaximal exercise capacity that reflects the level at which most activities of daily living are performed, predicts clinical events in cardiac patients, and is therefore a clinically meaningful outcome in cardiac rehabilitation studies.⁴²⁻⁴⁴ Participants will be asked to walk at their own maximal pace on an established course, covering as much ground as they can during the allotted time, without running.^{45,46} Performance will be measured by the total distance covered in feet. Blood pressure, oxygen saturation, and HR will be measured before, during, and/or after the test.

Physical function will be assessed using 2 performance-based measures and 1 self-report measure. The expanded Short Physical Performance Battery (**SPPB**) is a modified version of a widely used assessment of lower extremity physical function that consists of 3 standing balance tasks held for 10 seconds each (side-by-side, tandem and semi-tandem), two 4-m walk tests to assess usual gait speed, and 5 repeated chair stands. To minimize ceiling effects and maximize overall dispersion of test scores, the expanded SPPB increases the holding time of the semi- and full-tandem stands to 30 seconds and adds a single leg stand and a narrow walk test of balance (walking at usual pace within lines of tape spaced 20 cm apart). Expanded SPPB scores are continuous and range from 0 to 4, with higher scores indicative of better performance.⁴⁷ **Grip strength** will be measured twice in each hand using an isometric hydraulic hand

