subject random effect will be included to account for the fact that multiple measurements within a participant over time are not independent. Fixed effects will include sex and obesity severity (i.e., the randomization stratification factors), clinical site (WFBMC, DMC, or LMC), the baseline (pre-randomization) value, time (3 or 6 months), the group assignment, and the group by time interaction. Hypothesis tests for intervention effects at the 3- and 6-month study visits will be performed using contrasts of the 3- and 6-month intervention group means. The primary comparison will be based on an intervention contrast at 6 months. Overall comparisons between groups across follow-up visits will be obtained using a contrast to compare average effects across both follow-up visits. Associations with the stage of change (S-Weight) and P-Weight scores will be examined to determine their influence on recruitment, retention, adherence, CHD outcomes, and neurovascular outcomes. If a particular intervention group has a markedly higher dropout rate, we will attempt to identify baseline covariates that predict attrition in secondary analyses. If such covariates can be identified, the analysis of the outcome measure will adjust for those covariates. Other factors that may influence the measured responses to the interventions such as the number of comorbidities, socioeconomic status, time to enrollment, medication use, and magnitude of weight loss will also be evaluated. Differences in intervention process measures (e.g., total volume of exercise) and compliance measures (e.g., attendance at diet and exercise sessions) will also be examined to assess the extent to which these variables contribute to the outcomes.

Human Subjects Protection

Subject Recruitment Methods

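### Compliance is a ratio of session counts but is compared between arms by chi-square, with no unit of analysis and no participant-level cut-off

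*Combined protocol and SAP*

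**What the plan says.** The Primary Outcome section gives feasibility three components. Recruitment is the number randomized over the number eligible. Retention is "the proportion of randomized participants who return for follow-up testing", a yes/no per person. Compliance is "total number of exercise/counseling sessions attended divided by total number of sessions prescribed", a ratio of session counts. The plan expects this rate to reach at least 80%, but nowhere uses 80% to classify a participant as compliant.

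Statistical Analyses then names one test for the last two components: "Chi-square tests will be used to assess group differences in retention and compliance rates". It gives no unit and no cut-off for compliance.

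For the longitudinal outcomes, the same section adds a subject random effect to "account for the fact that multiple measurements within a participant over time are not independent". Nothing comparable is provided for compliance. The section also says that "compliance measures (e.g., attendance at diet and exercise sessions) will also be examined" for their contribution to the outcomes, without naming a unit or a test.

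The exercise schedule, under Cardiac Rehabilitation, is "three exercise sessions and one group health/nutrition education class per week for 12 weeks", after which "all participants will undergo an additional 12 weeks of supervised cardiac rehabilitation for a total period of 6 months". Individual counseling, described under Behavioral Modification, exists only in Rehab+WL.

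**The concern.** A chi-square test needs independent yes/no units. For compliance, the only counts the plan defines are sessions. One person's sessions are correlated: some people attend reliably, others do not, and someone who drops out misses everything afterwards. Pooling them makes 20 people per arm look like hundreds of independent observations.

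The alternative reading does not rescue the stated test. A participant's own attendance ratio is a fraction, and a fraction enters a chi-square only after it is cut into compliant and not compliant. Without a cut-off fixed in advance, that choice stays open until the data are seen.

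At stake is a false statement that adding weight loss changed attendance, or an interval that is far too narrow, in a pilot meant to inform a larger trial. This is the only between-arm test the plan states for compliance.

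**Working it through.** **The plan's own figure.** Sample Size says: "Based on a conservative dropout rate of 20%, we expect a final sample size of 16 per group". From 40 randomized, 40 × (1 − 0.20) / 2 = 16, so this reproduces. The documents give no significance level, power or ICC for the compliance comparison.

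**Inputs from the documents.** 20 per arm randomized (40 split equally), or 16 after dropout. Exercise sessions per person: m = 3 × 12 = 36 in the first 12 weeks. Attendance p = 0.80, the expected rate.

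**Assumptions.** Two-sided 5% level; m = 72 if three sessions per week continue for 24 weeks; ICC over a range; education classes not counted.

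**1. Type I error when sessions are pooled.** The design effect is DE = 1 + (m − 1) × ICC, and the real error is 2 × [1 − Φ(1.96 / √DE)]. For m = 36 and ICC 0.10, DE = 1 + 35 × 0.10 = 4.5, 1.96 / √4.5 = 0.924, and the error is 0.36. Beta-binomial simulation (20,000 null trials per setting, 20 per arm) agrees with the formula within 0.005:

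| ICC | 36 sessions | 72 sessions |
|---|---|---|
| 0 | 5% | 5% |
| 0.01 | 9% | 13% |
| 0.02 | 13% | 21% |
| 0.10 | 36% | 49% |
| 0.30 | 56% | 68% |

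With 16 per arm and ICC 0.01 to 0.30, the ranges are 9–57% and 14–68%. Counting counseling gives Rehab+WL about 12 + 6 = 18 further sessions, so 90 against 72; the error at ICC 0.10 is then 51–52%.

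**2. How much ICC dropout alone would create.** Suppose a fraction d leaves at a uniformly distributed time, attendance while in the study is q = 0.8 / (1 − d/2) and otherwise independent, and sessions after dropout count as prescribed. Then ICC = [q² × (1 − 2d/3) − 0.64] / 0.16. For d = 0.20, q = 0.889 and ICC = (0.790 × 0.867 − 0.64) / 0.16 ≈ 0.28.

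| Dropout | Implied ICC | Error, 36 sessions | Error, 72 sessions |
|---|---|---|---|
| 5% | 0.07 | 28% | 40% |
| 10% | 0.14 | 41% | 53% |
| 20% | 0.28 | 56% | 66% |

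If sessions after dropout are left out of the denominator, this source disappears and the error is about 5%.

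**3. Worked example.** Take 82.5% against 77.5% attendance, 36 sessions and 20 per arm, so 720 sessions per arm. Pooled, z = 0.05 / √(0.8 × 0.2 × 2 / 720) = 2.37 and p = 0.018. At ICC 0.10, z = 2.37 / √4.5 = 1.12 and p = 0.26.

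**4. Participant as the unit.** Across these null settings with 20 per arm, a t-test on individual attendance proportions has error 2.9–5.1% and Wilcoxon 4.2–5.3%. In the beta-binomial settings, a chi-square on participants cut at 80% has 4.2–5.3%, so it is valid. It costs power, shown here at ICC 0.10 for assumed differences:

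| Attendance | Sessions | t-test | Chi-square, 80% cut-off |
|---|---|---|---|
| 85% v 70% | 36 | 89% | 73% |
| 85% v 70% | 72 | 92% | 77% |
| 85% v 75% | 36 | 60% | 43% |
| 85% v 75% | 72 | 64% | 47% |

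**The case against.** The strongest reply is that the plan never says sessions will be pooled. Attended over prescribed is equally how one person's attendance is calculated. The chi-square sentence pairs compliance with retention, a participant-level measure, and the subject random effect shows that the authors understand within-person dependence. The 80% figure is an obvious candidate cut-off, and with it the planned chi-square is valid. On that view the gap is one missing definition, not a wrong test.

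Part of this stands. Pooling is a reading, not a stated analysis, and every inflated error rate above is conditional on it. But the definition speaks of totals and sits beside the study-level ratio of randomized to eligible, and 80% is worded as an expected rate. The participant-level reading still needs a rule that the plan does not contain.

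The ICCs are assumed, and the dropout figures need uniform timing and post-dropout sessions in the denominator. The plan calls 20% conservative and expects less, so that row is the upper end. These limits are accepted; the direction does not depend on them.

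The power comparison uses differences that are not in the plan, in a pilot not designed for power. It supports preferring the uncut proportion; it does not show that a pre-specified cut-off would be wrong.

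Finally, Statistical Analyses does foresee examining differences in diet and exercise attendance, which partly anticipates separating the two. It names no test or unit there, so it does not close the gap.

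**Conclusion.** The concern holds and should be fixed. Applied to the ratio as defined, the stated test gives a p-value that is too small whenever attendance is correlated within a person. The only valid chi-square reading needs an unstated cut-off, which in the settings examined loses about 15 to 18 points of power against a t-test.

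On the pooled reading, with 20 per arm and 80% attendance, type I error runs from 9% to 56% with 36 sessions and from 13% to 68% with 72, over assumed ICCs of 0.01 to 0.30. Any positive ICC pushes it above 5%.

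The practical consequence is modest. Feasibility is judged on rates, the 80% expectation does not rest on this comparison, and no decision rule uses its p-value. Confidence is medium because the plan does not state which reading is intended.

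**What to change.** Keep chi-square for retention. For compliance, amend Statistical Analyses as follows:

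- Name the participant as the unit. Compute each participant's attendance proportion and compare arms by t-test or Wilcoxon, or by a binomial model clustered on participant, with a 95% confidence interval.
- State whether sessions after dropout count as prescribed.
- Keep the overall compliance rate as the descriptive feasibility measure. Also report the between-arm comparison on exercise sessions, which both arms are prescribed, and describe counseling attendance in Rehab+WL only.
- If a compliant yes/no comparison is preferred, fix the cut-off in advance.

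The cost is two or three sentences and no new data, because relating attendance to outcomes already requires a value per participant. The price is a wider, honest interval. With 20 per arm, the half-width for the difference is 1.96 × √[2 × 0.8 × 0.2 × DE / (20m)]:

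| Sessions | Pooled (DE = 1) | ICC 0.02 | ICC 0.10 | ICC 0.30 |
|---|---|---|---|---|
| 36 | 4.1 points | 5.4 | 8.8 | 14.0 |
| 72 | 2.9 points | 4.5 | 8.3 | 13.8 |
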